On three evenings over the next 7 days, the children will eat a standard high protein/high fat meal. The evenings will not be set, but will depend on the child and family schedule. The study meal will not be eaten on the evening that the CGM is inserted as sensor accuracy takes 24 hours to maximise accuracy. The child and family will be able to choose which days during the study period on which they complete the study meals but will be advised to avoid days when the participant has undertaken lots of exercise, is hypoglycaemic immediately before the meal or has had frequent hypoglycaemic episodes, or has been unwell.

The standard meal will be a portion controlled gluten-free meal provided and delivered by Wiltshire Farm Foods consisting of a meat-based main course and dessert. These will be kept frozen until used by participants and prepared according to manufacturer instructions. These meals come in two sizes which allow portion sizes to be adjusted for different ages of child, but the proportions of fat, protein and carbohydrate will be kept constant for each child, and by definition the meals will be high in protein and high in fat.

Insulin doses with the standard meal will be given according to calculations carried out by the dietitian and administered in one of three ways.

The three evenings in random order will be as follows -

1. Insulin units based on ICR and fat/protein dose given together immediately before the meal [control meal].
2. Insulin units based on ICR given immediately before the meal plus extra insulin for fat/protein units given 1 hour after the first meal dose.
3. Insulin units based on ICR given immediately before the meal plus extra insulin for fat/protein units given 2 hours after the first meal dose.

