Participants will be asked not to give a correction dose before the meal if the BG level is between 7-12mmol/l as this would interfere with the analysis. They will be asked, if possible, not to carry out the test meals if their pre-meal BG is greater than 12 mmol/l. But if they have to do the test meal with a high pre-meal BG (above 12 mmol/l) they will be instructed to give their usual correction bolus in addition to the prescribed insulin dose for the test meal. This data will be analysed separately. If BG is below 4mmol/l (hypoglycaemic) or above 16mmol/l participants will be asked to abandon the study evening and repeat on another evening. Full written instructions will be provided to the family for all aspects of the insulin dosing for the study meals.

During the study on the standardised meal days children will be instructed not to eat any food after the meal during the evening, and not to correct any later BG levels unless they are dangerously high (BG over 16 mmol/l with ketones over 0.5 mmol/l). If BG levels go low at any time (BG less than 4 mmol/l) children will be instructed to treat the hypoglycaemia according to their usual management, and omit

any further study doses of insulin if the hypoglycaemia occurs after a first study dose and a second is due. This data will be analysed separately. Children and families will be asked to complete diaries during the trial week.

At the end of the study period (the day after the third meal), children will come back to the research facility or clinic for the end of study visit (visit 3). A research nurse or dietitian will remove the CGM sensor and download the data onto a secure laptop. Children and their families will then be asked to complete a short questionnaire about the acceptability of using the extra insulin doses, and their perceptions as to whether there were any beneficial or adverse effects.

The study dietitian will calculate standard outcomes from each patient's sensor download and pass on anonymously to the study statistician to analyse the data.

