11.6. Inclusion in Analysis

All data available from all participants will be used for the analyses. If a child has become hypoglycaemic (BG $< 4.0 \text{ mmol/l}$) during the profile period then subsequent data will be analysed separately. If any child has had to treat a high BG level with additional insulin (except for a correction dose at the evening meal), then subsequent profile data will be analysed separately. However in either instance, the data up to the event will be included in all analyses. The two other meals would still be eligible for the study analyses if there were no similar events.

If there have been any protocol breaches, such as further food during the evening after the main meal, then all the subsequent data will not be used in the analysis for that meal. Education of the participants and parents will be vital to ensure that such eventualities are rare.

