20. APPENDIX B: AMENDMENT HISTORY

Amendment No.	Protocol Version No.	Date issued	Author(s) of changes	Details of Changes made
1	2	20/11/15	[name]	Minor typographical errors Additional Research Nurses added Confirmed protocol met REC recommendations to remove patient initials from all data collection
2	3	21/6/16	[name]	Adjusted the original calculation used in the protocol. This reduces the amount of additional insulin administered for fat and protein and therefore reduces the risk of hypoglycaemia in future participants. (Page 8 and Page 11) We also changed guidance for completing the study evenings following hypoglycaemic episodes immediately before the study meal – stating that in this incidence the meal should be abandoned. This also reduces the risk of hypoglycaemia afterwards. (Page 12) Minor changes were made to the flowchart to remove giving the voucher at visit 3 – this will now happen once all participants have completed the study at the end (Page 10)
3	4	1/4/17	[name]	Change of Chief Investigator
3	4	1/4/17	[name]	Clarification that the second insulin dose should be given at a time interval after the first insulin dose as there had been ambiguity from participants about the meaning of 'after the meal' Change in management of correction doses pre-evening meal. It has

				become clear that it will be very difficult to analyse change in BG level from pre-meal levels once a correction dose of insulin is given. So we have asked participants only to correct if BG above 12mmol/l and if possible to avoid doing the study on evenings when BG is above 12 mmol/l before the meal if possible. They should definitely not complete the meal if BG is above 16mmol/l
--	--	--	--	---

Protocol amendments must be submitted to the Sponsor for approval prior to submission to the REC committee or MHRA.

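### The timing comparison ignores whether glucose was already rising or falling before the first dose: avoidable noise in the primary comparison, with no bias shown

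*Combined protocol and SAP*

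**What the plan says.** The primary outcome (synopsis and section 5) is the mean glucose excursion over the 8 hours after the test meal. The secondary outcomes identify baseline as the pre-meal level.

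On insulin before the meal, section 6.3 asks participants "not to give a correction dose before the meal if the BG level is between 7-12mmol/l as this would interfere with the analysis". Above 12 mmol/l they are asked to avoid the test meal if possible; if it goes ahead, "they will be instructed to give their usual correction bolus in addition to the prescribed insulin dose for the test meal", and section 6.3 says those data are analysed separately. On level, "If BG is below 4mmol/l (hypoglycaemic) or above 16mmol/l participants will be asked to abandon the study evening and repeat on another evening". Appendix B gives the reason for the correction rule: "it will be very difficult to analyse change in BG level from pre-meal levels once a correction dose of insulin is given".

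On food, "children will be instructed not to eat any food after the meal during the evening". On the earlier part of the day, families "will be advised to avoid days when the participant has undertaken lots of exercise, is hypoglycaemic immediately before the meal"; frequent hypoglycaemia and illness are also listed. Recent rapid-acting insulin and recent food are not.

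Section 11.6 analyses separately the profile that follows extra insulin for a high reading, but adds an exemption: "except for a correction dose at the evening meal". Section 11.1 plans paired t tests or Mann-Whitney tests by timing and names no covariate.

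**The concern.** The plan's reason for restricting a pre-meal correction is that insulin already at work blurs the change from baseline. That reason applies equally to a correction or snack bolus given an hour or two before the meal. It also applies, in the other direction, to a snack or a treated low. A single reading between 4 and 12 mmol/l says where glucose is, not which way it is heading. An evening that starts at 9 mmol/l and falling is treated like one that starts at 9 and steady.

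Such evenings are plausible. Section 7.2 requires rapid-acting insulin before each meal. Families see the sensor readings and are asked to avoid test meals above 12 mmol/l. The trial itself asks whether moving a dose by 1 or 2 hours changes the curve, so it can hardly treat insulin given 1 or 2 hours before the meal as negligible.

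At stake is the precision of the primary comparison. The direction of glucose at baseline is also already measured: section 6.3 says the sensor records every 5 minutes, so the hour before the first dose holds about 60/5 = 12 readings. The plan does not use them.

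**Working it through.** **The plan's own figure.** Section 11.2 gives 36 children, 80% power, a difference of 2 mmol/L and a 5% level, but no SD, so 36 cannot be reproduced directly. Solving for the SD of a within-child difference between two timings:

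- Normal approximation: 2 × √36 / (1.960 + 0.842) = 12 / 2.802 = 4.28.
- Paired t, two-sided 5%, 35 df, noncentrality 2√36/SD: SD = 4.165, variance 17.34.

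The paired-t value is used below. Section 11.2 refers to the 5-hour excursion while the primary outcome is at 8 hours, so carrying this SD across is an assumption.

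**Noise from pre-meal state.** The documents give no frequency or size. Assume a share p of evenings is affected, each by c mmol/L on the 8-hour mean, independently of timing. The variance contributed to a within-child difference is 2p(1−p)c²:

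- p = 0.1, c = 1: 2 × 0.1 × 0.9 × 1 = 0.18
- p = 0.2, c = 2: 2 × 0.2 × 0.8 × 4 = 1.28
- p = 0.3, c = 3: 2 × 0.3 × 0.7 × 9 = 3.78

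Suppose the 17.34 already includes this noise. Power at n = 36 is then recomputed with SD = √(17.34 − v) for complete removal and √(17.34 − v/2) for half, where v is the contributed variance:

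| p, c | v | Share of 17.34 | Power, all removed | Power, half removed |
|---|---|---|---|---|
| 0.1, 1 | 0.18 | 1% | 80.4% | 80.2% |
| 0.2, 2 | 1.28 | 7% | 82.9% | 81.5% |
| 0.3, 3 | 3.78 | 22% | 88.6% | 84.3% |

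If instead the planning SD left this noise out, SD = √(17.34 + v). Power is then about 80%, 77% and 72% at n = 36, and 84%, 82% and 77% at the 40 to be recruited.

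**Bias.** The expected bias in a contrast is (difference between timings in the share of affected evenings) × c. With equal shares it is 0. Assumed differences of 10 to 20 points with c of 1 to 3 would give 0.10 × 1 = 0.1 to 0.20 × 3 = 0.6 mmol/L. Nothing in the documents supplies such a difference.

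**Would excluding affected evenings do better?** A pair survives only if both evenings are unaffected, so 36(1−p)² pairs remain:

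- p = 0.1: 36 × 0.81 ≈ 29 pairs, power about 71%
- p = 0.2: 36 × 0.64 ≈ 23 pairs, power about 63%
- p = 0.3: 36 × 0.49 ≈ 18 pairs, power about 58%

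These use the reduced SD, with the noise fully gone, and all are below the 80% from leaving the data alone. Exclusion is not a sound main analysis; adjustment is.

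**The case against.** The case for leaving the plan alone has several good parts.

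- **Randomisation.** The order is randomised (section 6.1) and fixed in a sealed envelope (section 8.3). The motive to correct early so that an evening stays below 12 mmol/l is the same for all three timings. This stands. A reader might infer that afternoon insulin biases the comparison because families know the order and choose the evenings. That is a possible route, but the documents give no reason for earlier intake to differ by timing and do not show that afternoon corrections occur.
- **Existing controls.** A reader might infer that a correction at the meal is the only thing controlled. That is too wide. The run-in week is meant to reduce high and low evening readings, evenings below 4 or above 16 mmol/l are abandoned, days with frequent lows are advised against, and later food and corrections are handled. The extra-insulin rule in section 11.6 has no start time and might be read to reach an afternoon correction, though not a snack or its bolus. None of this captures the direction of glucose at baseline.
- **Diaries.** Trial-week diaries exist, and section 9.3 has them record actual insulin doses. The form is not in the documents, so one cannot say that the necessary entries are missing.
- **Small gain.** A one-hour trend is only a proxy, so complete removal of the noise is unrealistic. The low and middle cases gain little. This stands, and it limits how strongly the point can be put.

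**Conclusion.** The gap is real and the remedy is cheap, but the effect is modest. The plan gives a reason for controlling insulin at work before the meal, then checks only the level at the meal and analyses the timings without regard to baseline direction. The consequence that can be supported is avoidable noise. On the assumed inputs, removing half of it adds about 0 to 4 points of power. About 9 points requires 30% of evenings affected by 3 mmol/L and complete removal. The figures rest on those inputs, on independence from timing, and on an SD inferred from a 5-hour calculation. Differential bias is not established.

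A related conflict needs settling. Section 6.3 says evenings with a correction at the meal are analysed separately, while section 11.6 exempts that correction from its separate-analysis rule. The two sections must be reconciled; this review takes no position on the clinical instruction.

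**What to change.** 1. **Main analysis (section 11.1).** Analyse the 8-hour mean excursion with a within-child model containing child, period and timing, and include each evening's pre-dose sensor trend as a pre-specified covariate. Define the trend as the change in CGM glucose over the hour before the first dose. It is measured before the timings diverge, so adjusting for it does not remove any effect of timing.
2. **Sensitivity analysis only.** Repeat the model without evenings where the diary shows a correction dose or food within one look-back period, the same for all children and fixed before the data are examined. The documents give no duration of insulin action, so the investigators must set and justify its length. These evenings stay in the main analysis.
3. **Diary detail.** Confirm that the trial-week diary captures the time and amount of the last rapid-acting dose and last food before each test meal.
4. **Consistency.** Reconcile sections 6.3 and 11.6 on evenings with a correction at the meal.

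The cost is a model in place of paired t tests and one degree of freedom. With 36 children and three evenings each, error df is 108 − 36 − 2 − 2 = 68 before the covariate and 67 after it. The sensor data are already downloaded, and no instruction to families on treatment changes.

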2. SYNOPSIS

Trial Title	Investigation of Appropriate Timing of Additional Insulin Dosing for Fat and Protein in Children with Type 1 Diabetes using Multiple Daily Injections	
Internal ref. no. (or short title)	Fat/Protein Study	
Clinical Phase	Phase 4	
Trial Design	Controlled observational study	
Trial Participants	Children aged 6 to under 18 years of age with type 1 diabetes (T1DM)	
Planned Sample Size	40	
Treatment duration	1 week	
Follow up duration	No follow-up at the end of the trial period	
Planned Trial Period	1 year	
	Objectives	Outcome Measures
Primary	To determine whether additional insulin boluses for the fat and protein content of a meal given before, one or two hours after a meal optimise post-prandial blood glucose levels in children with Type 1 diabetes using multiple daily injections?	Continuous subcutaneous glucose profiles will be examined to determine – 
 • mean post-prandial glucose excursion for 8 hours following the test meal
Secondary	To examine other indices of BG control following additional insulin boluses for the fat and protein content of a meal given before, one or two hours after a meal in children with Type 1 diabetes using multiple daily injections?	Continuous subcutaneous glucose profiles will be examined to determine – 
 • peak BG level • peak BG excursion from baseline (pre-meal BG level) • time of peak BG level from baseline measurement • Rate of BG excursion from baseline to peak • mean post-prandial glucose excursion for 5 and 12 hours following the test meal • area under the curve at time-points 0-3 hours, 3-5 hours, 5-8 hours, 8-12 hours post-meal • Time from baseline BG at which BG returns to baseline level
Investigational Medicinal Product(s)	Insulin	
Formulation, Dose, Route of Administration	Insulin Aspart (NovoRapid) given in a dose according to the protocol, subcutaneously	

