5. OBJECTIVES AND OUTCOME MEASURES

Objectives	Outcome Measures	Timepoint(s) of evaluation of this outcome measure (if applicable)

Primary Objective To determine whether additional insulin boluses for the fat and protein content of a meal given before, one or two hours after a meal optimise post-prandial blood glucose levels in children with Type 1 diabetes using multiple daily
	
Continuous subcutaneous glucose profiles will be examined to determine –
 
 mean post-prandial glucose excursion for 8 hours following the test meal 	
Continuous Glucose Monitoring profiles during the 12 hours following the test meals

[figure not shown]
injections?		

Secondary Objectives
 
To examine other indices of BG control following additional insulin boluses for the fat and protein content of a meal given before, one or two hours after a meal in children with Type 1 diabetes using multiple daily injections?
	
Continuous subcutaneous glucose profiles will be examined to determine –
 
 • peak BG level • peak BG excursion from baseline (pre-meal BG level) • time of peak BG level • timing of peak BG excursion 
area under the curve at time-points 0-3 hours, 3-5 hours, 5-8 hours, 8-12 hours post-meal
	
Continuous Glucose Monitoring profiles during the 12 hours following the test meals

Tertiary Objectives
 
1. To assess the acceptability of giving additional insulin doses for fat and protein to children using MDI
 
2. To assess the safety of giving additional insulin doses for fat and protein to children using MDI
	
1. Questionnaires to parents and children during and at the end of the study
 
2. All episodes of hypoglycaemia (BG less than 4 mmol/l) or hyperglycaemia (BG >12 mmol/l) either on CGM or self-monitoring of BG
	
Collection of data during and at the end of the study

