11.1. Description of Statistical Methods

Descriptive statistics will be used to describe the group demographics and outcomes.

The continuous glucose records will be analysed methodically by the CI, research dietitian and statistician. Data to be obtained include –

- pre-meal BG level
- peak BG level
- peak BG excursion from baseline at 3, 5, 8 and 12 hours following the meal
- time of peak BG level
- time of peak BG excursion
- area under the curve at time-points 0-4 hours, 4-6 hours, 6-8 hours, 8-12 hours post-meal

The relationship between the insulin timing and the mean change in postprandial blood glucose levels will be analysed and described.

Comparisons using paired t tests for normally distributed data, and Mann-Whitney U tests for non-parametric data will be used to examine the differences in areas under the postprandial BG curves and the postprandial BG levels by insulin timing.

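### Secondary outcomes that run past 8 hours can include breakfast and its insulin dose, because no rule ends the profile at the first morning food or insulin

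*Combined protocol and SAP*

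**What the plan says.** **Length of profile.** Section 5 evaluates the outcomes on "Continuous Glucose Monitoring profiles during the 12 hours following the test meals". The primary outcome stops earlier: "mean post-prandial glucose excursion for 8 hours following the test meal" (Synopsis). The secondary outcomes in the Synopsis include "mean post-prandial glucose excursion for 5 and 12 hours following the test meal" and "area under the curve at time-points 0-3 hours, 3-5 hours, 5-8 hours, 8-12 hours post-meal". They also include peak level, peak excursion, time of peak and return to baseline, with no shorter window stated. Section 11.1 divides the earlier hours differently but keeps an 8–12 hour AUC, and adds "peak BG excursion from baseline at 3, 5, 8 and 12 hours following the meal".

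**Food.** Section 6.3 says that "children will be instructed not to eat any food after the meal during the evening". Section 11.6 drops the later data for a meal after a protocol breach, and its example has the same limit: "such as further food during the evening after the main meal".

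**Insulin.** Section 11.6 analyses separately the data that follow hypoglycaemia, and the data that follow extra insulin given for a high glucose. It does not mention the meal dose at breakfast. Section 7.2 admits only children who take rapid-acting insulin before each meal.

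**Timing of the meal.** Section 6.3 leaves the days to the family: "The evenings will not be set, but will depend on the child and family schedule". No clock time for the meal is given anywhere in the text.

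**Default.** Apart from these exceptions, Section 11.6 uses whatever data exist.

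**The concern.** Twelve hours from an evening meal can reach past the next breakfast. A child who eats the test meal at 20:00 and has breakfast with its usual dose at 07:00 breaks no rule in the text. Hours 11 to 12 of that profile then reflect a different meal and a different injection, but they are analysed as response to the test meal.

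The exposed outcomes are the 12-hour mean excursion, the 8–12 hour AUC and the 12-hour peak excursion. Peak level, time of peak and return to baseline are also exposed if they are taken over 12 hours. Section 4 gives better glucose up to 12 hours after the meal as the trial's aim, so the late window is one that the trial means to report on. Time of peak is the most fragile of these outcomes, because one breakfast peak that exceeds the test-meal peak replaces it and moves the recorded time by hours.

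The gap also leaves a judgement open. The study dietitian derives the outcomes from each download (Section 6.3) and the trial is open-label (Section 8.3). Without a rule, whether a morning rise counts would be decided case by case by someone who may know the dosing order.

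**Working it through.** The plan gives no figure for this point, so there is none to reproduce. The check is clock arithmetic.

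**Inputs from the documents.** Profile length is 12 hours (Section 5), the last AUC window is 8–12 hours (Synopsis, Section 11.1), the primary window is 8 hours (Synopsis), and the outcome used for power is a 5-hour mean (Section 11.2).

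**Assumptions, because the documents give no values.** Breakfast at 07:00, with a range of 06:30 to 09:00. Test meal started between 17:00 and 21:00. Average breakfast effect of 2 to 4 mmol/l during the overlap, net of the breakfast dose.

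**Step 1. Overlap with the 12-hour profile.**

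Overlap = max(0, meal start + 12 h − breakfast time). Its share of the 8–12 hour window is overlap / 240 min.

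| Meal start | Overlap, breakfast 07:00 | Share of 8–12 h window |
|---|---|---|
| 19:00 | 0 min | 0% |
| 19:30 | 30 min | 30/240 = 12.5% |
| 20:00 | 60 min | 60/240 = 25% |
| 20:30 | 90 min | 90/240 = 37.5% |

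The threshold moves with breakfast. Overlap begins for meals started after 18:30 with a 06:30 breakfast, after 19:00 with 07:00, and after 20:00 with 08:00. For a 20:00 meal, the overlap is 90 min with a 06:30 breakfast, 60 min with 07:00, 30 min with 07:30, and none from 08:00 on. A meal started at 18:30 or earlier has no overlap anywhere in the assumed range.

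**Step 2. Overlap with the primary and the powered outcome.** The latest assumed meal is 21:00. Adding 8 hours gives 05:00, and adding 5 hours gives 02:00. Both precede the earliest assumed breakfast at 06:30, so the overlap is 0 min throughout. The AUC windows that end by 8 hours are clean for the same reason.

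**Step 3. Size on an affected evening.**

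Shift in the 8–12 h mean = rise × overlap in hours / 4. Shift in the 12-hour mean = rise × overlap in hours / 12.

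| Overlap | 8–12 h mean, rise 2 to 4 mmol/l | 12-hour mean, rise 2 to 4 mmol/l |
|---|---|---|
| 30 min | 0.25 to 0.5 | 0.08 to 0.17 |
| 60 min | 0.5 to 1.0 | 0.17 to 0.33 |
| 90 min | 0.75 to 1.5 | 0.25 to 0.5 |

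At 60 min the 8–12 h AUC gains 2 to 4 mmol/l·h. For scale only, 0.17 to 0.33 is about 8% to 17% of the 2 mmol/l difference in Section 11.2, which refers to the 5-hour mean.

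**Step 4. Effect on a comparison within a child.** If all three evenings have the same overlap and the same breakfast effect, the shift cancels in each paired difference. If one evening overlaps by 60 min and the other two do not, each difference that involves that evening moves by 0.5 to 1.0 mmol/l on the 8–12 h mean.

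**Step 5. Time of peak.** As an illustration, if the test-meal peak is at 4 h and a higher breakfast peak comes at 11.5 h, the recorded time moves by 11.5 − 4 = 7.5 h. This happens only if the breakfast peak is the higher one.

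**The case against.** A reader might infer that breakfast biases the comparison of timings. The documents do not show this. Order is randomised within each child (Sections 6.1 and 8.3), and nothing ties late meals or early breakfasts to any one condition. A difference between a school day and a weekend falls on the conditions at random. Families do know the order from the start (Section 8.3) and choose the days (Section 6.3). They could therefore place the evening with a later injection on a particular kind of day, so some alignment with condition is possible, but it is not shown. On the text, the expected effect is mainly noise.

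A reader might also infer that the background predicts a fat and protein effect lasting 12 hours, which would make the last hour critical. Section 4 states 12 hours as an aim. The evidence it cites is of raised glucose up to 6 hours.

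The food clause in Section 11.6 is only an example, so other breaches could count. This does not close the gap: nothing forbids breakfast, so eating it is not a breach of any kind.

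Section 4 describes monitoring as lasting overnight into the next morning, which suggests a profile that ends about then. Trial-week diaries with actual insulin doses (Sections 6.3 and 9.3) and waking and pre-meal finger-pricks (Section 6.3) may already hold much of what a cut-off needs. Both points stand, and they make the repair easier, but neither sets an end point.

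The flow chart and the families' written instructions are not in the text available for review. A breakfast instruction there cannot be ruled out, so the certainty extends only to the protocol text and the analysis rules in Section 11.6.

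Finally, the size rests on assumed clock times and an assumed rise, and how often overlap would occur is unknown. That also stands.

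**Conclusion.** The point holds for secondary outcomes that extend past 8 hours, and only for those. The text lets an ordinary breakfast and its dose fall inside the analysed profile, and no rule in Section 11.6 removes them. The figures in the working show that this can matter on an evening with a late meal: a shift of up to 1.0 mmol/l in the 8–12 h mean for a 20:00 meal and a 07:00 breakfast, if the assumed rise of 2 to 4 mmol/l is about right. Families who eat early would see no effect at all.

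The expected consequences are less precision in the late-window comparisons and unreliable times of peak. Systematic bias towards one timing is not established. The primary result and the stated power are not called into question by this point. It is worth correcting because the affected outcomes are pre-specified and the correction is cheap.

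**What to change.** 1. In the trial-week diary, record the clock time of the test meal and of the first food or rapid-acting insulin next morning.
2. In Section 11.6, state that each profile ends at that first morning food or insulin if it comes before 12 hours.
3. Compute the late outcomes over the window common to the child's three evenings: the 8–12 hour AUC or its per-hour mean, the 12-hour mean, the 12-hour peak and the time of peak. Per-hour means keep children with different window lengths comparable. Apply the same cut to return to baseline, and record a meal that has not returned by then as not returned within the observed time.
4. In Section 11.5, state that a profile shortened in this way counts as complete over its common window, so that it is not dropped from the complete-case analysis or filled in by imputation.

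Asking families to start the three test meals at similar times would help, but it is optional.

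The cost is two diary entries and a short addition to Sections 11.5 and 11.6. Some profiles will end before 12 hours, so the late outcomes rest on slightly less data, and their definitions must be written as up to 12 hours or first morning food or insulin, whichever is earlier. The primary analysis does not change.
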